9.3. Sample Size Sensitivity

For Cohorts 1,2, 3a and 4-8 the sensitivity of the precision estimate is calculated with respect to three different sample sizes and between subject CV as presented below in [Table 10](#).

Table 10 Sample Size Sensitivity for Cohorts 1,2, and 4-8 Precision Estimates

Between subject CV, CVb (%)	Between subject standard deviation, SDb	Sample size	Actual distance from mean to limits (log transformed scale)	Distance from Point estimate (%)
20	0.198	4	0.315	37
	0.198	6	0.208	23
	0.198	8	0.166	18
30	0.294	4	0.468	60
	0.294	6	0.309	36
	0.294	8	0.246	28
40	0.385	4	0.613	85
	0.385	6	0.404	50
	0.385	8	0.322	38

For the assumed variability of AUC and C_{max} respectively, for Cohort 3, the impact of different numbers of evaluable participants on the precision estimates and 90% confidence intervals were assessed with the results presented in [Table 11](#).

Table 11 Sample size sensitivity for fixed within subject coefficient of variation

Parameter	CVw	Sample size (n)	Point estimate (PE) fed vs fasted	Precision Estimate	90% CI of PE
AUC	20%	6	1	26%	(0.74, 1.35)
		8	1	21%	(0.79, 1.27)
		10	1	18%	(0.82, 1.22)
		12	1	16%	(0.84, 1.19)
		14	1	14%	(0.86, 1.16)
		16	1	13%	(0.87, 1.15)
	30%	6	1	41%	(0.59, 1.69)*
		8	1	32%	(0.68, 1.47)
		10	1	27%	(0.73, 1.37)
		12	1	24%	(0.76, 1.32)
		14	1	22%	(0.78, 1.28)
		16	1	20%	(0.8, 1.25)
Cmax	30%	6	1	41%	(0.59, 1.69)
		8	1	32%	(0.68, 1.47)
		10	1	27%	(0.73, 1.37)
		12	1	24%	(0.76, 1.32)
		14	1	22%	(0.78, 1.28)
		16	1	20%	(0.8, 1.25)
	40%	6	1	57%	(0.43, 2.33)
		8	1	44%	(0.56, 1.79)
		10	1	37%	(0.63, 1.59)
		12	1	33%	(0.67, 1.49)
		14	1	29%	(0.71, 1.41)
		16	1	27%	(0.73, 1.37)

* Based on a CVw of 30%, it is estimated that for a sample size of 6 participants, the lower bound of the 90% CI will be within approximately 41% of the point estimate and the upper bound of the CI within 69%, i.e. assuming a point estimate of 1 (i.e, no difference) the CI would be as wide as (0.59, 1.69).

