9.2. Sample Size Determination

The planned sample size is up to 80 participants for this study (8 participants each for Cohorts 1, 2 and 3a and up to 16 participants for Cohort 3) and up to 40 participants for the MAD part (8 participants into each of Cohorts 4-8). Additional participants may be recruited as replacements for withdrawn participants. Cohort 1 and 2 are split by a 2:6 for ratio of placebo participants to active participants per period. For Cohort 3 the regimens are split by a 1:1:1:1 ratio.

For Cohorts 1,2, 3a and 4-8 assuming a between-participant CV (CV_b) of 30% for clearance, it is estimated that, with 6 participants per dose, the 95% confidence interval around the mean of the clearance for a dose would lie within 36% of the point estimate ([Table 10](#)).

Sample size in Cohort 3 was calculated based on the precision estimate for fed versus fasted status. The objective of Cohort 3 (SAD part) is to determine if food effects the PK of GSK3494245 and to inform the dosing regimen for the MAD part. A precision estimate was therefore used to determine the sample size, based on assumed within subject coefficient of variation (CV_w) for AUC of 20% and C_{max} of 30% respectively. A maximum of 16 participants will be recruited with the aim of getting evaluable data from 12 participants. If the estimates for the CV_w decrease following review of the data from Cohorts 1 and 2, then fewer participants may be recruited, with the aim of obtaining as few as 10 evaluable participants.

Assuming a point estimate for fed versus fasted status of 1 (i.e. no food effect), under the variability assumptions described above, and a sample of 12 evaluable participants, the precision estimates and 90% confidence intervals (CI) for AUC and C_{max} are:

Parameter	CVw	Sample size	Precision estimate	90% CI
AUC	20%	12	16%	(0.84, 1.19)
Cmax	30%	12	24%	(0.76, 1.32)

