	
 apparent terminal phase half-life ($t_{1/2}$) 
from MAD:
 
 Day 1 AUC(0-t), AUC(0-∞), AUC(0-tau), C_{max}, T_{max}, $t_{1/2}$, trough concentration (C_{tau}). 
Trough concentration (C_{tau}) samples collected on the specified days may be used to assess attainment of steady state.
 
To estimate the extent of accumulation after repeat dosing, the observed accumulation ratio for AUC (($RAUC_{(0-tau)}$)), C_{max} (RC_{max}) and C_{tau} (RC_{tau}) may be determined. To estimate time-invariance after repeat dosing, the ratio of AUC(0-tau) on Day 7 to AUC(0-∞) on Day 1 may be obtained. Time-invariance ratio calculation for TID regimen, if conducted, as AUC(0-tau) on Day 6 evening dose to AUC(0-∞) on Day 1
 
Statistical analyses of the pharmacokinetic parameter data will be the responsibility of Biostatistics, GlaxoSmithKline. No formal hypotheses will be tested. Pharmacokinetic data will be presented in graphical and/or tabular form and will be summarized descriptively. Full details on the statistical aspects will be detailed in the Reporting and Analysis Plan (RAP).
 
A population PK approach may be used if data permit. In this case the analysis may be reported separately from the clinical study report.
 
Estimand
 
Intercurrent events, the estimand strategy to handle these events and the changes to the respective analysis to implement the strategies will be highlighted in the RAP.
 
Food Effect (SAD part)
 
The effect of food on the pharmacokinetics of GSK3494245 will be examined. AUC(0-t), AUC(0-∞) and C_{max} of GSK3494245 will be analyzed after a \log_e-transformation of the data. An analysis of variance model will be fitted along with 90% confidence intervals using a mixed effects model, with fed/fasted condition as a fixed effect and participant as a random effect. Point estimates and corresponding 90% confidence intervals will be constructed for the comparisons of interest of GSK3494245 fed – GSK3494245 fasted, using the residual variance. These will then be back-transformed to provide point estimates and corresponding 90% confidence intervals for the geometric mean ratios fed: fasted.

Endpoint	Statistical Analysis Methods

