8.1. Sample Size Sensitivity

For Cohorts 1, 2, 3a and 4-8 the sensitivity of the precision estimate is calculated with respect to three different sample sizes and between subject CV as presented below in [Table 2](#).

Table 2 Sample Size Sensitivity for Cohorts 1, 2, 3a and 4-8 Precision Estimates

Between subject CV, CVb (%)	Between subject standard deviation, SDb	Sample size	Actual distance from mean to limits (log transformed scale)	Distance from Point estimate (%)
20	0.198	4	0.315	37
	0.198	6	0.208	23
	0.198	8	0.166	18
30	0.294	4	0.468	60
	0.294	6	0.309	36
	0.294	8	0.246	28
40	0.385	4	0.613	85
	0.385	6	0.404	50
	0.385	8	0.322	38

For the assumed variability of AUC and C_{\max} respectively, for Cohort 3, the impact of different numbers of evaluable participants on the precision estimates and 90% CIs were assessed with the results presented.

Sample size sensitivity for fixed within subject coefficient of variation.

Parameter	CVw	Sample size (n)	Point estimate. (PE) fed vs fasted	Precision Estimate	90% CI of PE
AUC	20%	6	1	26%	(0.74, 1.35)
		8	1	21%	(0.79, 1.27)
		10	1	18%	(0.82, 1.22)
		12	1	16%	(0.84, 1.19)
		14	1	14%	(0.86, 1.16)
		16	1	13%	(0.87, 1.15)
	30%	6	1	41%	(0.59, 1.69) *
		8	1	32%	(0.68, 1.47)
		10	1	27%	(0.73, 1.37)
		12	1	24%	(0.76, 1.32)
		14	1	22%	(0.78, 1.28)
		16	1	20%	(0.8, 1.25)
Cmax	30%	6	1	41%	(0.59, 1.69)
		8	1	32%	(0.68, 1.47)
		10	1	27%	(0.73, 1.37)
		12	1	24%	(0.76, 1.32)
		14	1	22%	(0.78, 1.28)
		16	1	20%	(0.8, 1.25)
	40%	6	1	57%	(0.43, 2.33)
		8	1	44%	(0.56, 1.79)
		10	1	37%	(0.63, 1.59)
		12	1	33%	(0.67, 1.49)
		14	1	29%	(0.71, 1.41)
		16	1	27%	(0.73, 1.37)

* Based on a CVw of 30%, it is estimated that for a sample size of 6 participants, the lower bound of the 90% CI will be within approximately 41% of the point estimate and the upper bound of the CI within 69%, i.e., assuming a point estimate of 1 (i.e., no difference) the CI would be as wide as (0.59, 1.69).

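### The 90% confidence intervals printed for the Cohort 3 food-effect comparison are miscalculated and too wide; the precision percentages and the cohort size stand

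*Protocol*

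**What the plan says.** Protocol 9.2 sizes Cohort 3 on the precision of the fed versus fasted comparison, using an assumed "within subject coefficient of variation (CV_w) for AUC of 20% and C_{max} of 30% respectively". On recruitment it says: "A maximum of 16 participants will be recruited with the aim of getting evaluable data from 12 participants". Recruitment may be lower, aiming for as few as 10 evaluable, if the CVw estimates fall after review of Cohorts 1 and 2.

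The reference case is a ratio of one ("Assuming a point estimate for fed versus fasted status of 1 (i.e. no food effect"), for which "the precision estimates and 90% confidence intervals (CI) for AUC and C_{max} are" tabulated at n=12: AUC 16%, (0.84, 1.19); Cmax 24%, (0.76, 1.32).

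Protocol Table 11 extends this to n = 6 to 16, with AUC at CVw 20% and 30% and Cmax at 30% and 40%. Its footnote puts the 41% on the lower side and 69% on the upper side: the "lower bound of the 90% CI will be within approximately 41% of the point estimate and the upper bound of the CI within 69" per cent. SAP 8 and 8.1 repeat the same figures, and the SAP footnote also says that "the CI would be as wide as (0.59, 1.69".

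The planned analysis is on the log scale. Protocol 9.5.2 says of the estimates: "These will then be back-transformed to provide point estimates and corresponding 90% confidence intervals for the geometric mean ratios fed: fasted". SAP 7.2.2 does the same.

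**The concern.** For a log-scale analysis with a point estimate of 1, the limits are exp(-h) and exp(+h), where h is the log-scale half-width. The upper limit then lies further from 1 than the lower limit, by exp(h) - 1 against 1 - exp(-h). The printed intervals are reciprocal, as they should be, but they pair each precision percentage with the lower limit. If that percentage is really the upper-side distance, both limits of every interval are wrong.

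These are the intervals a reader will use to judge what Cohort 3 can show about food, and the obvious reference when deciding between 10 and 12 evaluable participants. Intervals that are too wide make the cohort look less informative than it is.

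**Working it through.** **Inputs.** CVw of 20%, 30% and 40%; n of 6, 8, 10, 12, 14 and 16; point estimate 1; 90% two-sided interval (protocol 9.2 and 9.3). Log-scale analysis with back-transformation (protocol 9.5.2, SAP 7.2.2). Neither document states the degrees of freedom or the standard error behind the tables. I used n-1 and SDw × sqrt(2/n), and the first step tests that choice.

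**Formulas.** SDw = sqrt(ln(1 + CVw²)), which gives 0.198, 0.294 and 0.385. h = t(0.95, n-1) × SDw × sqrt(2/n).

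**Step 1: reproduce the precision estimates as exp(h) - 1.**
- AUC, CVw 20%, n=12: h = 1.796 × 0.198 × 0.408 = 0.145; exp(h) - 1 = 15.6%, printed 16%.
- Cmax, CVw 30%, n=12: h = 1.796 × 0.294 × 0.408 = 0.215; exp(h) - 1 = 24.0%, printed 24%.
- CVw 30%, n=6: h = 2.015 × 0.294 × 0.577 = 0.342; exp(h) - 1 = 40.7%, printed 41%.

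All 18 distinct rows reproduce to the printed percent (24 rows are printed, but the CVw 30% block appears twice). The column is therefore the distance to the upper limit. Protocol Table 10 uses the same upper-side convention: exp(0.309) - 1 = 36%.

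**Step 2: reproduce the printed intervals.** With p the rounded precision estimate, all 18 equal (1 - p, 1/(1 - p)):
- 1 - 0.16 = 0.84 and 1/0.84 = 1.19
- 1 - 0.24 = 0.76 and 1/0.76 = 1.32
- 1 - 0.41 = 0.59 and 1/0.59 = 1.69

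At CVw 40%, n=6, the unrounded p of 56.5% would give an upper limit of 2.30. The rounded 57% gives 1/0.43 = 2.33, which is the printed value. So the intervals were built from the precision column, not from h.

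**Step 3: the intervals that follow from h.** None of the 18 printed intervals matches (exp(-h), exp(h)) at either limit.

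| n | CVw 20%: printed | from h | CVw 30%: printed | from h | CVw 40%: printed | from h |
|---|---|---|---|---|---|---|
| 6 | (0.74, 1.35) | (0.79, 1.26) | (0.59, 1.69) | (0.71, 1.41) | (0.43, 2.33) | (0.64, 1.57) |
| 8 | (0.79, 1.27) | (0.83, 1.21) | (0.68, 1.47) | (0.76, 1.32) | (0.56, 1.79) | (0.69, 1.44) |
| 10 | (0.82, 1.22) | (0.85, 1.18) | (0.73, 1.37) | (0.79, 1.27) | (0.63, 1.59) | (0.73, 1.37) |
| 12 | (0.84, 1.19) | (0.86, 1.16) | (0.76, 1.32) | (0.81, 1.24) | (0.67, 1.49) | (0.75, 1.33) |
| 14 | (0.86, 1.16) | (0.88, 1.14) | (0.78, 1.28) | (0.82, 1.22) | (0.71, 1.41) | (0.77, 1.29) |
| 16 | (0.87, 1.15) | (0.88, 1.13) | (0.80, 1.25) | (0.83, 1.20) | (0.73, 1.37) | (0.79, 1.27) |

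For the footnote case, 1 - 0.71 = 29% on the lower side and 1.41 - 1 = 41% on the upper side.

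**Step 4: size.** At n=12 the interval width falls from 0.35 to 0.29 for AUC and from 0.56 to 0.43 for Cmax. Under these inputs the printed intervals carry about 93% to 99% confidence (94.6% for AUC and 95.7% for Cmax at n=12).

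**Step 5: could another formula explain the printed intervals?** A search over 240 combinations of degrees of freedom, SE factor, SD definition and t quantile found none that reproduces the CI column. The best put 7 of 18 rows within 0.01 and matched no precision estimate.

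**The case against.** **The sizing basis is intact.** Protocol 9.2 sizes the cohort on the precision estimate, and 16% and 24% are correct as upper-side distances. This stands. A reader might infer that the design precision as a whole is wrong or that the cohort is the wrong size. The documents do not support that: only the CI columns and the footnote's assignment of percentages to sides are wrong.

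**No decision is shown to change.** Neither document sets a CI width or limit for choosing 10 or 12, and the stated trigger is a fall in CVw. No hypothesis is tested, and the reported interval will come from the observed data. This also stands. A reader might infer that the error bites hardest at the down-sizing choice, but it shrinks as n rises and CVw falls. The most extreme row, n=6 at CVw 40%, lies below the SAP's floor of 10 evaluable and above the assumed variability. What remains is that, at the assumed CVw, the correct n=10 intervals are slightly tighter than those printed for n=12, which a user of the table cannot see.

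**Degrees of freedom.** SAP 7.2.2 adds a period effect, so a reader might prefer n-4. That is not needed here. The protocol's own food-effect model has no period term, and only n-1 reproduces the precision column. On n-4 the footnote case would be (0.61, 1.64), or 39% and 64%, and the n=6, CVw 20% interval would be (0.72, 1.40), wider than the printed one. The statement that every printed interval is too wide is therefore tied to n-1.

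**Conclusion.** The Cohort 3 CI columns in protocol 9.2 and 9.3 and SAP 8 and 8.1, and the Table 11 footnote with its SAP counterpart, are wrong as written. An upper-side distance was treated as a lower-side distance and then inverted. At the assumed CVw the limits are out by 0.02 to 0.08 at n=12 and by 0.03 to 0.10 at n=10, always in the direction of too wide.

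The corrected values rest on n-1 degrees of freedom and SE = SDw × sqrt(2/n). These are inferred, but they match all 18 distinct precision estimates. The error is conservative. Cohort 3 is not undersized, and neither enrolment nor the planned food-effect analysis needs to change.

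**What to change.** In protocol 9.2 and 9.3 and SAP 8 and 8.1:
- Replace each Cohort 3 90% CI with (exp(-h), exp(h)), as tabulated above.
- State the degrees of freedom and SE formula used.
- Label the precision estimate as the distance to the upper limit.
- Change the footnote to a lower bound within about 29% and an upper bound within about 41%, with interval (0.71, 1.41), on n-1 degrees of freedom.
- Use the corrected table when choosing 10 or 12 evaluable participants.

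The cost is a table and text edit in two documents.

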9.4. Populations for Analyses

For purposes of analysis, the following populations are defined:

Population	Description
Screened	All participants who were screened for eligibility
Enrolled	
 All participants who passed screening and entered the study. Included are: Randomized Participants 
Note: screening failures (who never passed screening even if rescreened) and participants screened but never enrolled into the study (Reserve, Not Used) are excluded from the Enrolled population as they did not enter the study.

Safety	
 All randomized participants who received at least one dose of study treatment. This population will be based on the treatment the participant actually received. 
Note: Participants who were not randomized but received at least one dose of study treatment should be listed.

PK	All participants in the Safety population who had at least 1 non-missing PK assessment (Non-quantifiable [NQ] values will be considered as non-missing values).

9.5. Statistical Analyses

The statistical analysis plan will be finalized prior to database release (DBR) and it will include a more technical and detailed description of the statistical analyses described in this section. This section is a summary of the planned statistical analyses of the most important endpoints including primary and key secondary endpoints.

Further details including strategies for intercurrent events (related to COVID-19 or not), visit windows etc. if applicable will be described in the analysis plan.

9.5.1. Safety Analyses

The primary analyses are to evaluate safety and tolerability of single and repeat doses of GSK3494245.

The safety population will be used for the primary analyses.

Endpoint	Statistical Analysis Methods
Primary	
Safety and tolerability data comprising of
 
 • adverse events • clinical laboratory data • physical examinations • vital signs • 12 lead ECGs • 24-48 hr telemetry 
will be presented in tabular and/or graphical format and summarized descriptively according to GSK's Integrated Data Standards Library (IDSL) standards.
 
Additional plots will be created using the data from Cohort 3 to assess changes in certain lab parameters with respect to the food effect and presence/absence of the drug. Further details will be provided in the Reporting and Analysis Plan (RAP).

9.5.2. Pharmacokinetic (PK) Analyses

All PK analyses will be performed on the PK Population.

Endpoint	Statistical Analysis Methods
Secondary	
Pharmacokinetic analysis will be the responsibility of the Clinical Pharmacology Modeling and Simulation Department, (CPMS), GlaxoSmithKline. Plasma GSK3494245 concentration-time data will be analyzed by non-compartmental methods with WinNonlin 8.0 or higher.
 
From the plasma concentration-time data, the following PK parameters will be determined, as data permit:
 
from SAD:
 
 • maximum observed plasma concentration (C_{max}) • time to C_{max} (T_{max}) • area under the plasma concentration time curve [AUC(0-t) and AUC(0-∞)]

Endpoint	Statistical Analysis Methods
	
 apparent terminal phase half-life ($t_{1/2}$) 
from MAD:
 
 Day 1 AUC(0-t), AUC(0-∞), AUC(0-tau), C_{max}, T_{max}, $t_{1/2}$, trough concentration (C_{tau}). 
Trough concentration (C_{tau}) samples collected on the specified days may be used to assess attainment of steady state.
 
To estimate the extent of accumulation after repeat dosing, the observed accumulation ratio for AUC (($RAUC_{(0-tau)}$)), C_{max} (RC_{max}) and C_{tau} (RC_{tau}) may be determined. To estimate time-invariance after repeat dosing, the ratio of AUC(0-tau) on Day 7 to AUC(0-∞) on Day 1 may be obtained. Time-invariance ratio calculation for TID regimen, if conducted, as AUC(0-tau) on Day 6 evening dose to AUC(0-∞) on Day 1
 
Statistical analyses of the pharmacokinetic parameter data will be the responsibility of Biostatistics, GlaxoSmithKline. No formal hypotheses will be tested. Pharmacokinetic data will be presented in graphical and/or tabular form and will be summarized descriptively. Full details on the statistical aspects will be detailed in the Reporting and Analysis Plan (RAP).
 
A population PK approach may be used if data permit. In this case the analysis may be reported separately from the clinical study report.
 
Estimand
 
Intercurrent events, the estimand strategy to handle these events and the changes to the respective analysis to implement the strategies will be highlighted in the RAP.
 
Food Effect (SAD part)
 
The effect of food on the pharmacokinetics of GSK3494245 will be examined. AUC(0-t), AUC(0-∞) and C_{max} of GSK3494245 will be analyzed after a \log_e-transformation of the data. An analysis of variance model will be fitted along with 90% confidence intervals using a mixed effects model, with fed/fasted condition as a fixed effect and participant as a random effect. Point estimates and corresponding 90% confidence intervals will be constructed for the comparisons of interest of GSK3494245 fed – GSK3494245 fasted, using the residual variance. These will then be back-transformed to provide point estimates and corresponding 90% confidence intervals for the geometric mean ratios fed: fasted.

Endpoint	Statistical Analysis Methods
	
Dose Proportionality (SAD part)
 
Dose proportionality will be assessed following single doses of GSK3494245 for fasted and fed cohorts separately(SAD part) via analyses of AUC(0-∞) and C_{max}.
 
A statistical analysis will be performed using the power model. The analysis will be performed on log_e-transformed data. For each of these parameters a mixed effects model will be fitted with log_e (dose) as a fixed effect and individual participant fitted as random effects. Estimates of the mean slopes of log_e (dose) will be reported along with corresponding 90% confidence intervals (slope\approx1 implies dose proportionality).
 
Accumulation (MAD part)
 
The extent of accumulation of GSK3494245 will be based on AUC (RAUC_(0-tau)), C_{max} (RC_{max}) and Ctau (RCtau).
 
The focus of the statistical analysis will be to estimate the accumulation ratio, Ro, on the pharmacokinetics of GSK3494245. Following log_e-transformation, AUC(0-tau) on Day 1 and AUC(0-tau) on the day of last dose will be analysed by a mixed effect model, fitting fixed effect terms for dose, day, and day by dose interaction, and fitting subject as a random effect.
 
For each dose, point estimates and 90% confidence intervals for the differences “Day 7 - Day 1” (for BID) or “Day 6 evening dose – Day 1 morning dose” (for TID) will be constructed using the appropriate error term. The point estimates and associated 90% confidence intervals will then be exponentially back-transformed to provide point and 90% confidence interval estimates for the ratios “Day 7: Day 1” (for BID) or “Day 6- Day 1” (for TID) for each active dose. If both the dose and day by dose interaction terms are not significant, a single point estimate and confidence interval pooled across all doses will also be constructed.
 
RC_{max} and RCtau will be estimated in a similar approach.
 
Steady State analysis (MAD part)
 
Steady state will be assessed following repeat dose of GSK3494245 (MAD part) via analyses of trough plasma concentration (Ctau)
 
A statistical analysis will be performed using mixed effect model on log_e transformed endpoint. A mixed effects model will be fitted with log_e (dose) as a fixed effect and subject fitted as random effect. The coefficients of the slopes for the day effect on log scale for each dose, along with corresponding 90% confidence intervals, will be used to determine whether steady state was achieved.

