Table 6 list the proposed dose levels for the MAD part of the study, together with exposure predictions (based on current study data from the SAD part up to 160mg) and expected safety cover for the 95th percentile of the population. Dose levels are only illustrative and actual doses might slightly differ once complete PK up to the highest dose in the SAD part of the study is available. However, the starting dose level for MAD will not exceed 30 mg BID or TID. It should be noted that calculated steady state plasma AUC_{24h} exposure on Day 7 will be used as part of PK stopping criteria following repeat dosing. PK sampling on Day 7 at steady state is proposed for 0-12h for BID dosing or 0-6h for TID dosing (in the event that TID schedule is selected). Hence, AUC_{24h} (Day 7) will be derived as $2 \times AUC_{12h}$ or $3 \times AUC_{6h}$ for BID or TID dosing, respectively.

Table 4 **Projected plasma GSK3494245 AUC_{0-∞} and C_{max} (mean and 95th percentile) following single oral doses of GSK3494245 in scenario 1, with Fold Cover to preclinical NOAEL**

Dose (mg)	Predicted Human Plasma Exposures*				Safety Margins with respect to NOAEL [#]			
	AUC _{0-∞} (ng×h/mL)		C _{max} (ng/mL)		AUC _{0-∞} (ng×h/mL)		C _{max} (ng/mL)	
	mean	p95	mean	p95	mean	p95	mean	p95
20 ^s	1209.8	1983.8	130.7	199.8	40.3	24.5	46.7	30.5
60 ^s	3642.1	6033.8	395.9	570.0	13.4	8.1	15.4	10.7
120 ^s	7284.3	12067.6	791.7	1140.1	6.7	4.0	7.7	5.4
200	11968.9	19589.5	1309.4	1964.2	4.1	2.5	4.7	3.1
300	17995.6	28360.9	1938.2	2841.8	2.7	1.7	3.1	2.1
400	23699.1	37665.2	2585	3755	2.1	1.3	2.4	1.6
500	30185.2	49827.2	3193.2	4727.6	1.6	1	1.9	1.3
600	36198.1	58042	3909.9	5640.9	1.3	0.8	1.6	1.1

*The predicted human exposures are in blood and the animal exposures are in plasma. Human Blood to plasma ratio (B/P ratio = 0.88) is used for conversion of predicted blood exposures to obtain human plasma exposures.

[#]NOAEL exposures in female minipig: AUC = 48700 ng×h/mL; C_{max} = 6100 ng/mL. Safety margin = NOAEL exposure parameter value/predicted human plasma exposure parameter.

^sDose not included in simulations, exposure derived proportionally from simulated doses.

Table 5 **Projected plasma GSK3494245 AUC_{0-∞} and C_{max} (mean and 95th percentile following single oral doses of GSK3494245 in scenario 2, with Fold Cover to preclinical NOAEL**

Dose (mg)	Predicted Human Plasma Exposures*				Safety Margins with respect to NOAEL [#]			

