	AUC _{0-∞} (ng×h/mL)		C _{max} (ng/mL)		AUC _{0-∞} (ng×h/mL)		C _{max} (ng/mL)	
	mean	p95	mean	p95	mean	p95	mean	p95
20 ^s	552.8	906.5	86.8	133.2	88.1	53.7	70.3	45.8
60 ^s	1664.4	2757.2	262.3	381.5	29.3	17.7	23.3	16.0
150	4009.6	6737.1	646	957.5	12.1	7.2	9.4	6.4
300	8223.5	12960.2	1288.3	1874.8	5.9	3.8	4.7	3.3
450	12248.4	19950.1	1943.3	2991.7	4	2.4	3.1	2
650	17669.2	27663.7	2752.4	4091.4	2.8	1.8	2.2	1.5
900	24980.4	39885.6	3858.9	5501.1	1.9	1.2	1.6	1.1
1200 ^s	33082.9	53046.1	5186.9	7484.8	1.5	0.9	1.2	0.8

*The predicted human exposures are in blood and the animal exposures are in plasma. Human Blood to plasma ratio (B/P ratio = 0.88) is used for conversion of predicted blood exposures to obtain human plasma exposures.

[#]NOAEL exposures in female minipig: AUC = 48700 ng×h/mL; C_{max} = 6100 ng/mL. Safety margin = NOAEL exposure parameter value/predicted human plasma exposure parameter.

^sDose not included in simulations, exposure derived proportionally from simulated doses.

Figure 3 GSK3494245 predicted human systemic plasma exposures ($AUC_{0-\infty}$ & C_{max}) in scenario 1 and scenario 2 after single dose at various doses with anticipated variability

Scenario 1: CL=3.81 mL/min/kg and F=80%

Scenario 2: CL=6.67 mL/min/kg and F=64%

[figure not shown]

Table 6 Proposed dose levels for the MAD part of the study with exposure predictions and expected tox cover for the 95P of the population

BID Dose (mg)	Total Daily Dose (mg)	Cmax (ng.mL)		AUC0-24 (ng h/mL)		Tox cover for P95 to NOAEL	
		Mean	95 th percentile	Mean	95 th percentile	Cmax	AUC0-24h
30	60	464.1	891.4	1819	3282	6.8	14.8
60	120	862.4	1637	3828	6854	3.7	7.1

BID Dose (mg)	Total Daily Dose (mg)	Cmax (ng.mL)		AUC0-24 (ng h/mL)		Tox cover for P95 to NOAEL	
		Mean	95 th percentile	Mean	95 th percentile	Cmax	AUC0-24h
120	240	1603	3102	8057	14610	2.0	3.3
180	360	2303	4567	12450	22954	1.3	2.1
240	480	2978	6042	16955	31744	1.0	1.5

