- Data from all available doses will be considered. An unstructured covariance structure will be considered for the G matrix describing the between subject variability. If this model fails to converge, alternative covariance structures may be considered such as Variance Component, Compound Symmetry, etc. Akaike's Information Criteria (AIC) will be used to assist with the selection of covariance structure.
- The Kenward and Roger method for approximating the denominator degrees of freedom and correcting for bias in the estimated variance-covariance of the fixed effects will be used.

- Distributional assumptions underlying the model used for analysis will be examined by obtaining a normal probability plot of the residuals and a plot of the residuals versus the fitted values (i.e., checking the normality assumption and constant variance assumption of the model respectively) to gain confidence that the model assumptions are reasonable.
- If there are any departures from the distributional assumptions, alternative transformations, such as data squared or square root of data, will be explored.

Model Results:

Adjusted geometric means for each dose will be presented along with the standard errors (SE) and 90% CIs. Estimated treatment ratios to reference dose (First or lowest dose of each part) and corresponding 90% CI will also be presented.

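### A power-model slope near 1 is read as dose proportionality without using the dose range or the width of the slope's 90% CI

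*Protocol*

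**What the plan says.** Dose proportionality after single doses is a secondary objective (Protocol section 3, SAP 1.1.1). Protocol 9.5.2 models log AUC(0-∞) and log Cmax on log dose with a random participant effect, separately for fasted and fed cohorts. The slopes "will be reported along with corresponding 90% confidence intervals", followed by a parenthetical note that a slope of about 1 "implies dose proportionality". SAP 7.3.2 repeats that note under its model results and adds period as a fixed effect.

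The same Protocol section states "No formal hypotheses will be tested". Neither document gives limits for the slope, a rule for using the interval, or a link to the range of doses studied. SAP 7.3.2 does provide "Estimated treatment ratios to reference dose" with 90% CIs, but only in the ANOVA that replaces the power model if it does not converge.

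**The concern.** A power-model slope has no fixed practical meaning until the dose range is known. The same slope can be a negligible departure over a 2-fold range and a material one over a 20-fold range. In this study the range is open: the dose escalation committee sets the doses, optional cohorts may be added, and the fasted and fed slopes may cover different ranges.

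The note also attaches to the point estimate. An imprecise slope that happens to fall near 1 would attract the same reading as a precise one. At stake is the stated conclusion on a secondary objective, in a study meant to inform dose choice in later studies.

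**Working it through.** **1. Checking the plan's own figures.** The ends of Table 6 in Protocol 4.5.3 read "30 60 464.1 891.4 1819 3282 6.8 14.8" and "240 480 2978 6042 16955 31744 1.0 1.5" (BID dose, daily dose, Cmax mean and 95th percentile, AUC0-24 mean and 95th percentile, then the two covers). At 240 mg BID, cover = NOAEL / 95th percentile: 6100/6042 = 1.01 and 48700/31744 = 1.53, as printed. Table 10 also reproduces: with CVb 30% and n = 6, exp(2.571 × 0.294/√6) − 1 = 36%.

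**2. Slopes implied by the Table 6 means.** The range is 240/30 = 8-fold.
- AUC0-24: ln(16955/1819)/ln 8 = 1.073
- Cmax: ln(2978/464.1)/ln 8 = 0.894

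Between adjacent rows the slopes stay at 1.073–1.074 and 0.893–0.894, so the means follow power laws closely.

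**3. Exposure per mg.** The ratio of highest to lowest dose is r^(slope − 1).
- AUC0-24: 8^0.073 = 1.165, or +16.5% (60.6 to 70.6 per mg of BID dose)
- Cmax: 8^(−0.106) = 0.802, or −19.8% (15.47 to 12.41 per mg)

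The two shifts run in opposite directions.

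**4. Expected precision of the fasted slope.** Taken from the plan: two cohorts of 8, each participant on three of four ascending doses plus placebo, 6 active per level (2 × 4 × 6 = 48 active profiles); CVw 20% for AUC and 30% for Cmax, and CVb 30% for clearance (Protocol 9.2). Assumed: eight log-spaced levels from 20 to 160 mg, which is 8-fold from the stated starting dose to the highest dose behind Table 6; CVb 40–45% as a less favourable case (40% also appears as a sensitivity value in Table 10).

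The variances are ln(1 + CV²). The SE of the slope comes from generalised least squares with a random participant intercept. The half-width is the SE times an approximate t multiplier: 1.70 without period, and 1.761 (14 df) with period, because the slope then rests largely on the contrast between cohorts.

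| CVb / CVw | SE, no period | 90% half-width | SE, with period | 90% half-width |
|---|---|---|---|---|
| 30% / 20% | 0.0748 | 0.127 | 0.1326 | 0.233 |
| 40% / 20% | 0.0800 | 0.136 | 0.1691 | 0.298 |
| 30% / 30% | 0.0974 | 0.166 | 0.1426 | 0.251 |
| 40% / 30% | 0.1068 | 0.182 | 0.1771 | 0.312 |
| 45% / 30% | 0.1104 | 0.188 | 0.1943 | 0.342 |

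Period costs this much precision because dose ascends with period within each cohort.

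**5. What this means per mg.** Suppose the observed slope is exactly 1 over 8-fold. A half-width of 0.13 gives a 90% CI for the high-to-low ratio of 8^(±0.13) = 0.76 to 1.31. A half-width of 0.19 gives 0.67 to 1.48. With period, 0.23 gives 0.62 to 1.61 and 0.34 gives 0.49 to 2.03.

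**6. Comparison with a conventional band.** The documents set no band. If 0.80–1.25 were used, the slope limits would be 1 ± ln(1.25)/ln r, which is ± 0.107 at 8-fold and ± 0.070 at 24-fold. At 24-fold (an assumed range) the half-widths without period are 0.083–0.123. Every fasted case exceeds its margin.

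**The case against.** The plan is one of estimation. The slope's 90% CI is a required output, no pass/fail decision depends on the note, and a reader who knows the doses can compute r^(slope − 1). SAP Table 1 derives dose-normalised Cmax and AUC that are not marked as listing-only, so a shift per mg would be visible in the summaries. All of this stands and limits the consequence. It does not supply what is missing, because the plan still attaches a conclusion to a slope without saying how the interval or the range enters it.

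Several stronger readings are tempting, and the documents do not support them:
- **That slopes of 1.07 and 0.89 would be declared proportional.** With about 1 undefined, they could be called either way. At 8-fold both point ratios (1.165 and 0.802) even fall inside 0.80–1.25.
- **That exposure per mg shifts by as much as 29%.** This needs an assumed 24-fold range: 24^(−0.106) = 0.71 for Cmax. Table 6's own range gives 17% and 20%.
- **That Table 6 shows the SAD result.** It projects BID steady-state AUC0-24 and Cmax for the MAD part, informed by SAD data up to 160 mg. The analysis at issue uses observed single-dose AUC(0-∞) and Cmax. The single-dose projections in Tables 4 and 5, simulated with dose-independent bioavailability, have slopes of 0.994–0.999.
- **That the label would drive dose selection.** Protocol 7.1.1 projects exposure for the next dose from the fitted model, not from a verdict of proportionality.

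**Conclusion.** The point holds as a gap in interpretation. For a secondary objective, both documents read a slope near 1 as proportionality without using the dose range or the precision of the slope. The Table 6 slopes show that values which might pass as about 1 can mean +17% and −20% per mg over 8-fold, and the plan does not say how it would describe them.

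For the fasted cohorts over 8-fold, the expected half-width of about 0.13–0.19, or 0.23–0.34 under the SAP's model with period, is too wide for a point estimate near 1 to establish proportionality. These half-widths rest on the plan's CVw of 20–30% and CVb of 30%, an assumed CVb of 40–45%, log-spaced doses, complete data and approximate t multipliers. A wider dose range would narrow the slope interval.

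**What to change.** In Protocol 9.5.2 and SAP 7.3.2, replace the note on slopes near 1. For each parameter and each food state:
- state the lowest and highest dose analysed;
- report the estimated ratio of dose-normalised geometric means, highest to lowest dose, r^(slope − 1), with the 90% CI obtained by transforming the slope limits in the same way;
- word the conclusion from that interval and range, for example as the change per mg over the range that the data do and do not rule out.

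A formal acceptance band such as 0.80–1.25 is optional. In every fasted case above, it would be expected to return an inconclusive result even with an observed slope of 1. A fed cohort over an assumed 8-fold range, with CVb 30%, CVw 20% and no period term, would just fit: 1.75 × 0.0549 = 0.096 against 0.107.

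The cost is a few sentences in each document, with no new data and no new model. The downside is that the conclusions will be more cautious.
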